3.3. Rationale for trial design

Trilaciclib has conducted a number of clinical studies in the United States and Europe, all clinical trials were conducted according to standard operating procedures of the sponsor and/or contract research organization in compliance with Good Clinical Practice for the design, conduct, and analysis of clinical trials. All trials were conducted with the approval of the local

ethics committee or institutional review board. Among them, three randomized, double-blind phase II clinical trials in patients with small cell lung cancer (SCLC) confirmed that Trilaciclib administered in combination with chemotherapy (including 1st and 2nd/3rd lines of chemotherapy) can prevent or reduce chemotherapy-induced myelosuppression.

Based on the results of the clinical trials completed overseas, Trilaciclib has clear target of action, clear pharmacological action, good safety and tolerability, moderate protein binding rate, less DDI, intravenous administration is not affected by dietary absorption, and there is no significant difference in PK behavior between cancer subjects and healthy subjects. The exposure of Trilaciclib is found to be slightly higher in the Japanese population than in the European and American populations. Based on its good safety and tolerability and exposureefficacy relationship, it is considered that the exposure difference has no significant clinical significance, and dose adjustment is not recommended. Efficacy E-R analysis showed a flat pharmacodynamics-exposure profile. Doses administered between 200 and 280 mg/m² resulted in desirable responsiveness, including myeloprotective efficacy (exposure associated with ANC, severe neutropenia, and anemia occurrence) and antitumor activity (ORR, PFS, and OS). Taking into account the difference in drug exposure between subjects, the recommended clinical dose is 240 mg/m², which is the middle of the dose range of 200 to 280 mg/m². The E-R analysis of safety showed that the higher the exposure, the greater the probability of headache, phlebitis/thrombophlebitis, and injection site reactions, but these adverse reactions were of low grade and not clinically significant. Chinese and Japanese belong to Asian race, and the safety, exposure and efficacy of Trilaciclib in Chinese are expected to be similar to those in Japanese, supporting the safety and efficacy of this product in Chinese observed at the dose level of 240 mg/m^2 .

Trilaciclib has demonstrated efficacy and safety. At present, there is no evidence that the response of Chinese patients to drug treatment is different from that of overseas populations and may bring about safety and effectiveness impact.

At present, there is no relevant data on the use of Trilaciclib in the Chinese population in clinical trials of Trilaciclib. Therefore, in order to further evaluate the safety and efficacy of Trilaciclib in Chinese patients, a clinical trial including an open-label safety run-in and PK evaluation part and a randomized double-blind, placebo-controlled part is planned to be conducted in extensive stage small cell lung cancer in China.

3.4. End of study

The end of the study is defined as follows:

75% of subjects died, or 12 months after the last subject was enrolled, or the sponsor decided to terminate the study, whichever came first.

4. Study population

The proposed study population is patients with extensive stage small cell lung cancer.

4.1. Criteria for enrollment

Criteria for enrollment

Patients must meet all of the following inclusion criteria to be enrolled in the study:

- 1. Age \geq 18 years, male or female;
- 2. Histologically or cytologically confirmed extensive stage small cell lung cancer (ES-SCLC):
- Patients scheduled to receive carboplatin plus etoposide regimen: no prior systemic therapy (eg, chemotherapy or combined with immunotherapy);
- Patients scheduled to receive topotecan regimen: previously received 1/2 lines of chemotherapy or combined immunotherapy but not topotecan.

3. Presence of at least one radiation-naïve measurable lesion according to RECIST 1.1 criteria;

- 4. Hemoglobin \geq 90 g/L;
- 5. Neutrophil count $\geq 1.5 \times 10^9$ /L;
- 6. Platelet count $\geq 100 \times 10^9$ /L;
- 7. Creatinine $\leq 15 \text{ mg/L}$ or creatinine clearance (CrCl) $\geq 60 \text{ mL/min}$ (Cockcroft-Gault formula);
- 8. Total bilirubin $\leq 1.5 \times$ upper limit of normal (ULN);
- 9. Alanine aminotransferase (ALT) and aspartate aminotransferase (AST) \leq 3 × ULN or
- \leq 5 × ULN (for patients with liver metastases);
- 10. Albumin \geq 30 g/L;
- 11. ECOG PS score 0 2;
- 12. Expected survival time \geq 3 months;
- 13. Contraception:

Females: All females of childbearing potential must have a negative serum pregnancy test at screening and must use reliable contraception from signing of informed consent through 3 months after the last dose;

Male: Female partners of childbearing potential must use reliable contraception from signing the informed consent until 3 months after the last dose;

14. Understand and sign informed consent.

4.2. Exclusion criteria

1. Symptomatic brain metastases requiring local radiotherapy or hormonal therapy;

2. History of other malignancies, with the following exceptions: (1) clinically cured cutaneous basal cell or squamous cell tumors; (2) cured a) cervical cancer, b) prostate cancer, c) superficial bladder cancer; or (3) other solid tumors with a clinical cure time of more than 3 years;

3. Uncontrolled ischemic heart disease or clinically significant congestive heart failure (NYHA Class III or IV);

4. Stroke or cardiovascular or cerebrovascular event within 6 months prior to enrollment;

- 5. Severe active infection;
- 6. Psychological or other social factors causing insufficient trial compliance;

7. Other uncontrolled serious chronic diseases or conditions that, in the opinion of the investigator, would make participation in the trial inappropriate;

8. Known HIV infection, active hepatitis B (defined as positive HBV DNA), and hepatitis C (positive HCV RNA);

9. Radiation therapy within 2 weeks prior to enrollment;

10. Patients who have received cytotoxic drug therapy or investigational drug therapy within 4 weeks before enrollment, or non-cytotoxic anti-tumor drug therapy within 2 weeks;

11. Subjects in the first part of the study should not take strong or moderate inducers of CYP3A4 concomitantly within 4 weeks before taking the study drug, and strong inhibitors of CYP3A4 concomitantly within 2 weeks before taking the study drug;

12. Toxicity from prior anticancer therapy has not recovered to Grade 0 or 1 (except alopecia);

13. Hypersensitivity to the study drug (Trilaciclib, etoposide, carboplatin, topotecan) or components thereof;

14. Persons who are unable to act independently due to legal restriction or legal sense;

15. Pregnant or lactating women;

16. Not suitable for participating in this study in the investigator 's opinion.

5. Investigations treatment

5.1. Investigational drug

The study drug in this trial is: Trilaciclib/placebo, and the chemotherapy drugs for combination therapy are carboplatin, etoposide or topotecan.

Investigational product investigated:

Trilaciclib: provided by Jiangsu Simcere Pharmaceutical Co., Ltd., 300 mg/vial. Trilaciclib is a sterile powder, USP D-mannitol is added as cake formers, and citrate buffer is added to maintain the pH of the reconstitution at 4.0 to 5.0. The preparation of the study drug for reconstitution and dilution is described in detail in the Pharmacy Manual.

Trilaciclib placebo: The outer box of the placebo is designed to be consistent with the investigational product, Trilaciclib, and the contents of the box are filled with the same quality of padding (paper sheets), which will not break blind in appearance or handheld after sealing.Placebo was actually used to prepare 250 mL of 5% dextrose in water or saline (0.9% sodium chloride) as the vehicle used for Trilaciclib.

Background Therapy/Chemotherapy:

Carboplatin: Qilu Pharmaceutical Co., Ltd., 100 mg/10ml/box, solution

Etoposide: Jiangsu Hengrui Medicine, 100 mg/5ml/vial, solution

Topotecan: Jiangsu Aosaikang Pharmaceutical Co., Ltd., 2 mg/vial, solution

The structure and other pharmaceutical properties of chemotherapeutic drugs are detailed in the corresponding package inserts.

5.2. Study treatment regimen

The treatment regimen for this study is as follows:

Patients with 1st line ES-SCLC were treated with Trilaciclib or placebo in combination with carboplatin and etoposide (EC regimen); patients with 2nd/3rd line ES-SCLC were treated with Trilaciclib or placebo in combination with topotecan as detailed in Table 4 below:

Investigational drug		Usage	Period of administration		
1st line E	S-SCLC				
EC Regimen	Carboplatin	Target AUC = 5 (maximum dose 750 mg), intravenous drip over 30 min on Day 1 of each 21-day cycle;	Up to 6 cycles *		
Kegimen	Etoposide	100 mg/m ² , 21 days per cycle, intravenous drip over 60 min on days 1-3;	Up to 6 cycles *		
Trilaciclib/Placebo		240 mg/m ² , 21 days per cycle, 30 min intravenous drip before chemotherapy on Days 1-3 (try to complete the drip within 30 + 5 min due to PK study);	Up to 6 cycles *		
* OR Prog	gressive diseas	e, intolerable, withdrawal of consent, or investig	ator discontinuation prior to reaching		
6 cycles, v	whichever cam	e first			
2nd/3rd li	ine ES-SCLC	patients			
Topotecan		1.25 mg/m ² , 21 days per cycle, intravenous drip over 30 min on Days 1-5;	Until disease progression, intolerable, withdrawal of consent, or investigator termination of treatment, whichever came first		
Trilaciclib/Placebo		240 mg/m ² , 21 days per cycle, administered prechemotherapy over 30 min on Days 1-5 (infusion should be completed within $30 + 5$ min if possible due to PK studies).	Until disease progression, intolerable, withdrawal of consent, or investigator termination of treatment, whichever came first		

Table 4	Study	Treatment	Regimen

Date of medication visit is based on the first dose of investigational drug (Trilaciclib/Placebo) in each cycle (D1).

Notes:

Trilaciclib should be administered no more than 28 hours apart between infusions for 3 or 5 consecutive days, and no more than 4 hours between infusions of Trilaciclib and its subsequent injected chemotherapeutic agents (carboplatin or etoposide, or topotecan).

Trilaciclib should be used in combination with chemotherapy, that is, if EC regimen or topotecan is suspended or terminated, then trilaciclib should also be suspended or terminated. Similarly, subsequent chemotherapy should not be administered if the planned administration of Trilaciclib, i.e. Trilaciclib or placebo, has not been completed in any cycle.

Prophylactic use of any colony-stimulating factors (including granulocyte colonystimulating factor, granulocyte-giant cell colony-stimulating factor, erythropoiesis stimulating agent) was not permitted during Cycle 1, but could be used therapeutically if febrile neutropenia developed in patients with high-risk infections or risk factors indicating poor prognosis (sepsis, age > 65 years, neutrophils < 0.1×10^{9} /L, expected neutropenia lasting > 10 days, pneumonia, Version No.: V1.4, March 21, 2022 Confidential 59 / 111 invasive fungal infections, other clinically documented infections, fever requiring hospitalization, previous febrile neutropenia, etc.).

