	chemotherapy and prepared into 250 mL solution with 5% glucose injection or					
	normal saline and intravenously infused over 30 min (Because it involved PK					
	studies, try to complete the infusion within $30 + 5$ min).					
	Patients with 1st line ES-SCLC received up to 6 cycles of Trilaciclib or placebo					
	combined with carboplatin and etoposide or continued treatment until disease					
	progression, intolerability, withdrawal of consent, or investigator termination,					
	whichever came first; patients with 2nd/3rd line ES-SCLC received Trilaciclib or					
	placebo combined with topotecan until disease progression, intolerability,					
	withdrawal of consent, or investigator termination of treatment, whichever came first.					
	Notes:					
	Trilaciclib or placebo should be administered no more than 28 hours apart					
	between infusions for 3 or 5 consecutive days, and no more than 4 hours apart					
	between infusions of Trilaciclib and its subsequent chemotherapeutic agents injected					
	(with carboplatin and etoposide, or with topotecan).					
	Trilaciclib or placebo should be administered in combination with					
	chemotherapy, ie, if EC regimen or topotecan is suspended or discontinued, then					
	Trilaciclib or placebo should also be suspended or discontinued. Similarly,					
	subsequent chemotherapy should not be administered in any cycle if the planned					
	administration of Trilaciclib, i.e. Trilaciclib or placebo, has not been completed.					
	Prophylactic use of any colony-stimulating factors (including granulocyte					
	colony-stimulating factor, granulocyte-giant cell colony-stimulating factor,					

	erythropoiesis stimulating agent) was not permitted during Cycle 1, but could be used herapeutically if febrile neutropenia developed in patients with high-risk infections or risk factors indicating poor prognosis (sepsis, age > 65 years, neutrophils < 0.1×10^{9} /L, expected neutropenia lasting > 10 days, pneumonia, invasive fungal infections, other clinically documented infections, fever requiring hospitalization, previous febrile neutropenia, etc.).					
Study	Criteria for inclusion					
Population	Patients must meet all of the following inclusion criteria to be enrolled in the study:					
-	1. Age ≥ 18 years, male or female;					
	2. Histologically or cytologically confirmed extensive stage small cell lung					
	cancer (ES-SCLC):					
	• Patients scheduled to receive carboplatin plus etoposide regimen: no prior					

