5.4.2.2. Dose Modifications Based on Nonhematologic Toxicities

5.4.2.2.1. Hepatotoxicity

Dose modifications were based on hepatotoxicity occurring on the first day of the second and subsequent cycles as follows:

ALT/AST		Bilirubin	Carboplatin, etoposide and topotecan
Grade 1	AND/OR	\leq Grade 2	No change
Grade ≥ 2 a First occurrence Second occurrence Third occurrence	AND/OR	Grade ≥ 3 First occurrence Second occurrence Third occurrence	First Dose Reduction Second dose reduction Drug withdrawn

Table 9 Dose Modifications Based on ALT/AST and Bilirubin

A If liver metastasis is present at baseline and ALT/AST is Grade 2, a 1-grade worsening of the AE grade will result in a reduction of the first dose. If combined ALT/AST/combined bilirubin abnormalities occur, dose reduction is judged based on more severe cases.

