5.5.1.1. Dose interruption and termination of trilaciclib

For adverse events of special interest defined in Protocol Section 8.9, refer to Investigator 's Brochure Section 6 .2 to determine whether to stop the infusion or interrupt t rilaciclib treatment. Adverse events of special interest for which no action was given in the Investigator 's Brochure were handled as defined below:

- Other Toxicity Events: For severe (Grade 3) other toxicity events, hold Trilaciclib until the event recovers to ≤ Grade 1 or baseline, then consider resuming Trilaciclib; if Grade 3 events recur, permanently discontinue Trilaciclib. Trilaciclib was permanently discontinued for life-threatening (Grade 4) other toxicities.
- Hepatotoxicity: refer to treatment for "other toxic reactions" above.
- Embolic/Thrombotic Events, Venous: if related to the injection site, refer to Chapter 6 .2, "Injection site reaction/phlebitis/thrombophlebitis" of the Investigator 's Brochure; if not related to the injection site, refer to "Other toxicities" as described above.

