4.6.1. Extent of Study Drug Exposure

Duration of exposure to study drug during the treatment period and number of treatment cycles started will be summarized using descriptive statistics. Cumulative actual dose, cumulative planned dose for compliance, cumulative planned dose for compliance, medication compliance, and relative dose intensity will be summarized for the different study drugs (Trilaciclib or chemotherapy drugs), respectively.

- Duration of chemotherapy exposure (days) = date of first dose of study drug in last cycle date of first dose of study drug + 21 days
- Number of treatment cycles

A treatment cycle is considered to be started if the subject receives at least one dose of study drug (Trilaciclib/placebo or chemotherapy). Descriptive statistics will be used to summarize the number of cycles started and to summarize the counts and percentages of subjects by the number of cycles started.

Relative dose intensity (%) = (cumulative actual dose administered/cumulative planned dose administered) 100%,

If applicable, the proportion of subjects with dose reductions will be summarized separately by study drug. Number of events with dose reductions will be described and the number and percentage of subjects will be summarized by number of dose reductions.

- The dose of Trilaciclib/placebo will not be adjusted in this trial and will remain at 240 mg/m² unless safety data in Part 1 suggests that dose adjustment of Trilaciclib/placebo is warranted.
- Carboplatin, etoposide and topology are determined by comparing the actual dose on the

respective dosing pages of the current and previous cycles Dose reductions for ticam are shown in Table 1 for Cycle 2 and Day 1 of subsequent cycles.

Dose Level	Etoposide (mg/m ²)	Carboplatin AUC	Topotecan (mg/m ²)
Dose Level -1	Reduce to 75	Decreased to $AUC = 4$	1
Dose Level -2	Reduce to 50	Decreased to $AUC = 3$	0.8

Table 1 Dose reductions for carboplatin, etoposide and topotecan

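### Protocol 5.2, 5.5.1.1 and Table 9 conflict on whether chemotherapy continues when hepatotoxicity permanently stops trilaciclib/placebo at the first or second qualifying liver event

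*Protocol*

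**What the plan says.** Three parts of the protocol bear on a patient with severe liver toxicity.

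- **Trilaciclib/placebo (5.5.1.1).** Hepatotoxicity is listed by name and sent to the rule for other toxicities. Under that rule a first Grade 3 event leads to a hold. After that, "if Grade 3 events recur, permanently discontinue Trilaciclib". For Grade 4, "Trilaciclib was permanently discontinued for life-threatening (Grade 4) other toxicities". Causality is not a condition. The section names trilaciclib only, but 5.4.1 refers to it for trilaciclib/placebo and Part II is blinded, so I read it as covering both.
- **Link to chemotherapy (5.2, Notes; repeated in the synopsis under Study treatment).** "subsequent chemotherapy should not be administered if the planned administration of Trilaciclib, i.e. Trilaciclib or placebo, has not been completed in any cycle". The sentence before it sets the reverse link: if chemotherapy is suspended or ended, so is trilaciclib.
- **Chemotherapy (5.4.2.2.1, Table 9).** For findings on Day 1 of Cycle 2 and later, the ALT/AST trigger is "Grade ≥ 2 a First occurrence Second occurrence Third occurrence", and/or bilirubin Grade 3 or higher. The matching actions for carboplatin, etoposide and topotecan are "First Dose Reduction Second dose reduction Drug withdrawn". The trigger has no upper grade limit, and the table does not mention trilaciclib status.

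**The concern.** A site that reads 5.5.1.1 and then 5.2 would give no more chemotherapy to a patient whose trilaciclib/placebo has been permanently stopped. A site that reads Table 9 for the same patient would continue chemotherapy at a reduced dose. Nothing in the protocol says which text takes precedence. The choice decides whether a patient with extensive-stage disease keeps active chemotherapy once a supportive drug, or its placebo, has been stopped.

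It also reaches the analysis. All-cause chemotherapy dose reduction is a component of the major adverse hematologic event (MAHE) composite (Protocol 2.2; SAP 4.4.2.4). The number of cycles or the treatment duration in weeks enters the key secondary models as an offset (SAP 4.4.2.1, 4.4.2.2 and 4.4.2.4). Under Table 9 such a patient records a dose reduction and goes on accumulating cycles and weeks. Under 5.2 the patient does neither.

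**Working it through.** The plan gives no figure to reproduce here, so the check is one of logic: apply the three rules to the same liver history and see whether they can all be obeyed.

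**Individual histories (ALT/AST, each event found on Day 1 of Cycle 2 or later)**

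| Sequence of grades | 5.5.1.1: trilaciclib/placebo | 5.2: chemotherapy | Table 9: chemotherapy | Compatible? |
|---|---|---|---|---|
| 4 | permanent stop at event 1 | not given | first reduction | No |
| 3, 3 | permanent stop at event 2 | not given | second reduction | No |
| 2, 4 | permanent stop at event 2 | not given | second reduction | No |
| 2, 2, 4 | permanent stop at event 3 | not given | withdrawn at event 3 | Yes |
| 2, 2, 2 | no permanent stop triggered | not engaged by a permanent stop | withdrawn at event 3 | Yes |

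**All patterns of three qualifying events.** Each event is Grade 2, 3 or 4, so there are 3 × 3 × 3 = 27 sequences.

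- Stop at event 1 (first event Grade 4): 1 × 3 × 3 = 9.
- Stop at event 2: first event Grade 2 or 3 and second Grade 4, 2 × 1 × 3 = 6; or Grade 3 twice, 1 × 1 × 3 = 3. Total 9.
- Stop at event 3: 2-2-4, 2-3-3, 2-3-4, 3-2-3 and 3-2-4, so 5.
- No permanent stop: 2-2-2, 3-2-2, 2-3-2 and 2-2-3, so 4.
- Check: 9 + 9 + 5 + 4 = 27.

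Table 9 still continues reduced chemotherapy at events 1 and 2, so the conflict arises in 9 + 9 = 18 of 27 patterns. In the 5 patterns with the stop at event 3, Table 9 also withdraws chemotherapy and the rules agree. If every event is Grade 3 or 4 there are 2 × 2 × 2 = 8 patterns: 4 start with Grade 4 (stop at event 1), and 4 start with Grade 3 followed by Grade 3 or 4 (stop at event 2). All 8 conflict.

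These are counts of patterns. They say nothing about how often each occurs, and the documents give no Grade 3 or 4 hepatotoxicity rate from which to work that out.

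**A neighbouring rule to check.** Protocol 5.4.2.3 resumes treatment at the first and then the second dose reduction after other Grade 3 or 4 chemotherapy-related toxicity, and stops chemotherapy at the third occurrence. An event that is judged chemotherapy-related and also falls under 5.5.1.1 could meet the same clash, for example a Grade 4 venous thrombosis away from the injection site.

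**The case against.** The best defence is that the texts work at different levels. Table 9 sets a dose level and does not order treatment to continue, while 5.2 is a separate gate on whether chemotherapy is given at all, so the stricter rule governs. In addition, 5.4.2 requires drug-related non-hematologic toxicity to recover to Grade 1 or baseline before redosing, and 5.4.2.3 calls the chemotherapy adjustments recommended and lets the investigator choose otherwise. Finally, after a permanent stop no trilaciclib is planned any longer, so 5.2 might simply lapse.

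Little of this removes the conflict. The recovery condition only delays it. The flexibility in 5.4.2.3 covers chemotherapy dose adjustment and does not reach 5.2 or 5.5.1.1. The gate reading and the lapse reading lead to opposite outcomes for the same patient, and the documents choose neither. What does stand is that the conflict is narrow: Table 9 also serves Grade 2 ALT/AST, where no permanent stop arises, and it starts only at Cycle 2 Day 1.

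A reader might infer more, in three ways that the documents do not support.

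- **That every trilaciclib-only toxicity raises the same clash.** For an event outside Table 9 and not chemotherapy-related, only 5.2 speaks about chemotherapy, so no second rule contradicts it. Section 5.5.1.1 also refers some of these decisions to the Investigator's Brochure, which is not available here.
- **That the SAP foresees chemotherapy-only cycles.** SAP 4.6.1 says that "A treatment cycle is considered to be started if the subject receives at least one dose of study drug (Trilaciclib/placebo or chemotherapy"). That wording equally covers trilaciclib/placebo given without chemotherapy, and protocol deviations.
- **That the primary endpoint is biased towards trilaciclib**, because infusion-related reactions were more frequent on it (8.2% against 1.7%, Protocol 1.3.1) and missed Cycle 1 chemotherapy would lower the duration of severe neutropenia. Those figures count reactions, not stopped infusions, and no source says how many occur in Cycle 1. The same section reports fewer discontinuations of any study drug for adverse events on trilaciclib (9.0% against 11.0%). An infusion that fails on a later day also comes after Day 1 chemotherapy has been given.

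**Conclusion.** The inconsistency is real and should be corrected. A first Grade 4 or a second Grade 3 liver event, found on Day 1 of Cycle 2 or later and counting as the first or second qualifying occurrence, leaves the site with instructions that cannot all be followed. This rests on two readings: that 5.5.1.1 applies to trilaciclib/placebo alike, and that 5.2 continues to apply after a permanent stop. If the sponsor intends 5.2 to lapse at that point, the clash disappears, but the protocol has to say so.

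The main consequence is contradictory patient management. The statistical consequence is confined to patients with such events: whether a dose reduction is counted in MAHE, and how many cycles or weeks they add to the offsets. Its size and direction cannot be derived from the documents. No bias in the Cycle 1 primary endpoint is shown, because Table 9 does not govern Cycle 1 dosing. The one remaining route is the cycle-end date in SAP 4.1 (start of the next cycle, or Day 1 + 36 days if there is none), which matters only if severe neutropenia is still unresolved at the end of the cycle. An additional analysis assigning the worst duration of severe neutropenia to patients with missed chemotherapy is therefore not justified.

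**What to change.** Reconcile the Notes in 5.2 (and the matching synopsis text), 5.5.1.1 and Table 9, so that the protocol states one consequence for chemotherapy when trilaciclib/placebo is held and one when it is permanently stopped. Make the Grade 3 and 4 part of Table 9 agree with it. At the same time, check 5.4.2.3 for Grade 3 or 4 chemotherapy-related events that also fall under 5.5.1.1. Which rule prevails is for the sponsor's clinical team to decide.

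The cost is an amendment to protocol wording, with the usual ethics submission and notice to sites. It needs no new data, no change in sample size and no further analysis. The synopsis copied into SAP Appendix 1 should be brought into line when the SAP is next updated.
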